Non-specific immunotherapy with high-dose interferon has shown activity in disease-free survival in resected stage III disease, but its impact on overall survival in that setting, and in stage IV resected melanoma is less clear. A recent Phase III trial with pegylated interferon in stage III resected disease showed a significant long-term impact of this treatment on relapse-free survival, but not on overall survival. Subgroup analyses further showed that patients with macroscopic lymph node involvement did not derive a significant clinical benefit from this treatment, clouding the outcome for higher risk patients with stage IV resected disease and warranting the development of new treatment options for these patients. Active specific immunization against tumor antigens is certainly one such possible approach.

The recMAGE-A3 Antigen-Specific Cancer Immunotherapeutics (ASCI) has shown promising results in Phase II studies in stage IV melanoma. In a recent Phase II proof-of-concept trial of two different formulations of recMAGE-A3 ASCI in melanoma patients with early metastatic disease (GSK study 249553/008), a strong and robust immunological response was seen, and the safety of the treatments was considered acceptable, raising no specific safety concerns. Objective clinical response was observed for 5 of the 75 patients treated and another 7 patients showed disease stabilization (over periods varying between 5 and 12 months, some still ongoing). These preliminary findings support the development of recMAGE-A3 ASCI as adjuvant therapy for stage IV resected melanoma. A double-blind, randomized, placebo-controlled Phase III trial is currently evaluating the efficacy of recMAGE-A3 + AS15 ASCI versus placebo in patients with resected stage IIIB/C melanoma with macroscopic lymph node involvement (DERMA Study).

Additional support for developing recMAGE-A3 ASCI in the adjuvant melanoma setting may be found in a recent Phase II proof-of-concept trial of MAGE-A3 ASCI as adjuvant therapy for patients with resectable stage IB and II NSCLC. This study (GSK 249553/004) showed a relative reduction of the risk of disease recurrence of 27% in the group receiving the ASCI compared to the placebo group. The immunological responses observed in melanoma patients and NSCLC

CONFIDENTIAL

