All the patients developed a specific anti-MAGE-A3 antibody response and some of the tested patients also developed a cell-mediated immune response. The observation of the immune responses suggests that the ASCI combining recMAGE-A3 with the AS15 Adjuvant System induces a more robust immunological response, both humoral and cell-mediated.

The preliminary results of this trial showed an acceptable safety profile for the AS15 Adjuvant System and a potential for this ASCI formulation to induce a stronger immune response and lead to higher clinical activity. These findings confirm preclinical and clinical findings suggesting that AS15 is able to induce stronger immune and anti-tumor responses [Krieg, 2001; Meidenbauer, 2004; Ren, 2004; Speiser, 2005]. For this reason, GSK Biologicals has chosen recMAGE-A3 combined with AS15 as the preferred ASCI for development in melanoma and other cancers.

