4.3. Exclusion criteria

The following criteria should be checked at the time of randomization. **If any apply, the patient must not be included in the study:**

1. The patient has an ocular melanoma.
2. The patient has in-transit metastases.
3. The patient has been treated or is scheduled to be treated with an adjuvant anticancer therapy after the metastasectomy that qualifies the patient for inclusion in the present trial.
 - One prior systemic treatment with an immunomodulator (i.e., interferon, vaccine and/or anti-CTLA-4) after a previous surgery is permitted, provided that the last dose has been administered at least 45 days before randomization in the present trial.
 - Previous radiotherapy is permitted, provided that the treatment has been completed before the surgery that qualifies the patient for participation in the present trial .
4. The patient requires concomitant chronic treatment (more than 7 consecutive days) with systemic corticosteroids or any other immunosuppressive agents. The use of prednisone, or equivalent, at a dose of < 0.125 mg/kg/day (absolute maximum 10 mg/day) or topical steroids is permitted.
5. Use of any investigational or non-registered product (drug or vaccine) other than the study treatment within 30 days preceding the randomization or planned use during the study period.
6. The patient has a history of autoimmune disease such as, but not limited to, multiple sclerosis, lupus, and inflammatory bowel disease. Patients with vitiligo are not excluded.
7. The patient has a family history of congenital or hereditary immunodeficiency.

CONFIDENTIAL

8. The patient is known to be positive for Human Immunodeficiency Virus (HIV) or has another confirmed or suspected immunosuppressive or immunodeficient condition.
9. History of allergic disease or reactions likely to be exacerbated by any component of the treatments.
10. The patient has psychiatric or addictive disorders that may compromise his/her ability to give informed consent or to comply with the trial procedures.
11. The patient has concurrent severe medical problems, unrelated to the malignancy, that would significantly limit full compliance with the study or expose the patient to unacceptable risk.

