5.3.2. Randomization

Randomization will take place when it has been ascertained that the patient is fully eligible and at most 1 week before administration of the first injection of the study product, which will take place a maximum of 12 weeks after surgery.

Randomization of patients and treatment allocation at the investigator site will be performed utilizing the Moffitt Cancer Center's Subject Registration and Randomization Server, a web-based interactive randomization system (available 24H/day, 7D/week). It will be open-label and stratified on the following variables:

1. M Stage of the disease (M1a vs. M1b vs. M1c)
2. Prior treatment with IFN or anti-CTLA-4 (Yes or No)

The list of randomization numbers will be generated by the study statistician and passed on to Moffitt Research IT at MCC to be programmed in the automated web-based randomization system for this specific trial.

Randomization will be performed a maximum of 1 week before the first study treatment administration, which is assigned as Visit 1. Figure 3 presents the timeline for obtainment of patients' informed consent and the procedures to be performed before the beginning of the study.

After having verified that the patient is fully eligible and having obtained the patient's informed consent to participate in the study, the person in charge of the treatment administration will access the randomization system on Internet. Upon providing a patient number and the stage, and prior treatment with IFN or anti-CTLA-4, the randomization system will use the stratified randomization method to determine the treatment number to be used for the patient.

The actual treatment number used for each treatment administration of the patient must be recorded in the CRF. As soon as the targeted number of randomized patients has been reached, the enrollment of patients will be frozen. However, to allow patients at the screening phase or those who have signed the informed consent form at the time of enrollment hold to be enrolled, an over-enrollment of 5% (4 patients) will be allowed.

[figure not shown]

Figure 3. Timelines for pre-study procedures and obtaining informed consent.

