10.1.2. Immunogenicity endpoints

The primary laboratory endpoint is an assessment of the immunogenicity of the two regimens. Serum antibodies (such as Anti-MAGE-A3) seropositivity status (a seropositive patient is a patient whose titre is greater than or equal to the cut-off value) will be the primary immune endpoints assessed. Seropositivity will be assessed at baseline, after 2, 4, 6, 7 and 9 administrations, post-treatment (i.e., at concluding visit) and one year after concluding visit (i.e., at follow-up visit 2). Cellular immune assays will also be determined as a secondary endpoint. For methods of analysis, see Section 10.7.4.

Refer to Section 10.3 for details on the statistical analyses.

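### Prior vaccine recipients, MAGE-A3 vaccines included, are eligible but not stratified, and the primary antibody comparisons ignore baseline titre: some precision can be lost, though validity is not

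*Combined protocol and SAP*

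**What the plan says.** **Eligibility.** Exclusion 3 in section 4.3 states: "One prior systemic treatment with an immunomodulator (i.e., interferon, vaccine and/or anti-CTLA-4) after a previous surgery is permitted". A 45-day washout applies, and no antigen is excepted. Exclusion 5 adds only a short window: "Use of any investigational or non-registered product (drug or vaccine) other than the study treatment within 30 days preceding the randomization". Nothing in 4.2 or 4.3 asks about earlier MAGE-A3 immunisation or requires a negative antibody result at entry. The elimination list in 10.5 covers medication given during the study, not before it.

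**Stratification.** Section 5.3.2 stratifies on M stage and on "Prior treatment with IFN or anti-CTLA-4 (Yes or No"). Vaccine, the third therapy allowed by exclusion 3, is missing.

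**A possible source of exposure.** The Synopsis describes a phase III trial "currently evaluating the efficacy of recMAGE-A3 + AS15 ASCI versus placebo in patients with resected stage IIIB/C melanoma".

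**What the product does.** Section 1.2.3.3 reports from the earlier melanoma trial: "All the patients developed a specific anti-MAGE-A3 antibody response".

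**Endpoint and test.** Section 10.1.2 names "Serum antibodies (such as Anti-MAGE-A3) seropositivity status" as the primary immune endpoint, judged against a fixed cut-off. Section 10.3 compares the arms by a two-sample t test on log titre, with a Wilcoxon test if normality fails. Neither uses baseline. Baseline serum is nevertheless mandatory at Visit 1 (6.3.3, Table 8). Section 10.6.2 defines an antibody response that, for patients already at or above the cut-off, requires at least a doubling of their own baseline. Section 10.7.4 lists that measure beside geometric mean titre and seropositivity.

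**The concern.** The aim is to learn whether Poly IC:LC increases the antibody induced by the study product. A patient who has already received a MAGE-A3 product may start above the cut-off and respond as a boosted rather than a newly primed subject. On an absolute cut-off, that patient can count as positive without having responded to study treatment. In the titre comparison, a subgroup with higher titres widens the within-arm spread.

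Of the prior therapies that exclusion 3 allows, vaccine is the one that could act directly on the primary antibody endpoint, and it is the one left out of the stratification. A vaccine-only patient is coded No, so nothing in the randomisation keeps such patients from gathering in one arm. With about 20 patients per arm and a planned power of only 62%, there is little precision to give away.

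**Working it through.** **1. Reproduce the stated power (10.3).** The inputs are geometric means of 7,000 and 10,500, SD 0.28 on the log scale, 20 per arm and one-sided alpha 0.05.

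- Effect: δ = log10(10,500/7,000) = log10(1.5) = 0.176.
- Standard error: 0.28 × √(2/20) = 0.0885.
- Noncentrality: 0.176/0.0885 = 1.99. The critical t on 38 df is 1.686.
- Power by the noncentral t: 62.1%, against 62% stated.

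The other entries in that table also reproduce: 67.7, 73.7, 80.0 and 86.2%, against 68, 74, 80 and 86%. The base of the logarithm is not stated. Natural logs would give 99.8%, so base 10 is inferred.

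**2. Add a pre-immunised subgroup.** Let q be the share of patients previously immunised and s the shift of their analysis-visit titre in log10 units. The documents give neither, so both are assumptions. If the Poly IC:LC effect is the same in everyone:

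SD = √(0.28² + q(1−q)s²)

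| q | s | q(1−q)s² | SD | Power |
|---|---|---|---|---|
| 0, or any | any, or 0 | 0 | 0.280 | 62.1% |
| 5% | +0.1 | 0.0005 | 0.281 | 61.9% |
| 5% | +0.3 | 0.0043 | 0.288 | 60.1% |
| 5% | +0.5 | 0.0119 | 0.300 | 57.0% |
| 10% | +0.3 | 0.0081 | 0.294 | 58.5% |
| 10% | +0.5 | 0.0225 | 0.318 | 53.1% |
| 15% | +0.7 | 0.0625 | 0.375 | 42.6% |

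The last row is an outer corner, not an expectation.

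**3. Chance imbalance.** Two such patients in one arm of 20 and none in the other, at +0.5, move that arm's mean by 2/20 × 0.5 = 0.05 log10. That is 0.05/0.176 = 28% of the planned effect, in either direction.

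**4. Validity.** In simulations with 2, 4 or 6 such patients among 40 and a 2- to 5-fold titre shift (40,000 trials per setting), the unadjusted test kept a type I error of 4.8% to 5.1%.

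**5. Compare the remedies.**

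- *Adjusting* for prior MAGE-A3 immunisation returned power to about 61% in every simulated setting, given a common Poly IC:LC effect.
- *Dropping* the pre-immunised patients leaves SD 0.28 with fewer patients. With 2 of 40 dropped (19 per arm), power is 60.1%, the same as keeping them unadjusted at +0.3. With 4 of 40 dropped (18 per arm), power is 58.1%, against 58.5% for keeping them at +0.3 and 53.1% at +0.5. Exclusion from the analysis gains nothing at the smaller shift and recovers only part of the loss at the larger one.

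**The case against.** **The affected group may be empty.** No document says that such a patient was enrolled, or that this centre took part in the phase III trial. That trial is placebo-controlled, so only some of its participants received the product. Eligibility arises from silence about MAGE-A3, not from express permission. A patient who also had interferon or anti-CTLA-4 is coded Yes. All of this stands, and it is why a zero effect belongs in the range.

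**The titre shift may be nil.** Section 1.2.3.3 shows induction, not persistence or boosting. By 6 months a patient on schedule has had five adjuvanted doses, so titres in pre-immunised and naive patients could converge. Section 10.3 also gives 0.28 as an upper limit for the SD. This stands too.

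**Seropositivity is hardly affected.** A reader might infer that patients positive at entry distort the seropositivity comparison. The quotation from 1.2.3.3 points the other way: if nearly every treated patient seroconverts, a few who were positive beforehand change the post-treatment rates very little. The titre comparison is where precision is at risk.

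**The plan partly provides for this.** It collects baseline serum and defines a baseline-relative response, so it foresees patients who are positive at entry. But that response is not the named primary endpoint, and baseline does not enter the t test. The Wilcoxon fallback does not use it either.

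**Any unstratified covariate can be unbalanced in 40 patients.** True. What sets this one apart is that it may act directly on the primary endpoint and that exclusion 3 already names vaccine.

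**Conclusion.** The mismatch between exclusion 3 and stratification factor 2 is plain in the text, and neither primary antibody comparison uses the baseline titre. What follows is a possible loss of precision and exposure to chance imbalance. Power stays at 62% if there are no pre-immunised patients or no titre shift. It is about 60%, 57% and 53% for 5% at +0.3, 5% at +0.5 and 10% at +0.5 log10.

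These figures rest on assumed shares and shifts, a log10 scale, and a Poly IC:LC effect common to all patients. If Poly IC:LC added nothing in pre-immunised patients, the loss would be larger: simulated power is 57% to 51% with 2 of 40 at a 2- to 5-fold shift.

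A reader might go further and infer that the comparison is biased or its false-positive rate inflated. The documents do not support that: allocation is randomised and the simulated type I error holds. Nor do they establish that prior MAGE-A3 recipients will be antibody-positive at entry. That is a reasonable inference from 1.2.3.3, not a reported finding.

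**What to change.** **In any case (analysis):**

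- Record prior MAGE-A3 immunisation for every patient, with an unknown category for those from a blinded trial.
- In 10.3 and 10.7.4, adjust the log-titre comparison for baseline log titre or for prior MAGE-A3 immunisation. The half-cut-off rule in 10.6.2 already supplies a baseline value for patients below the cut-off.
- Use the baseline-relative antibody response of 10.6.2 as the binary measure in place of absolute seropositivity.
- Report the MAGE-A3-naive comparison as a sensitivity analysis, not as the main one.

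**Only if enrolment is still open:** add vaccine to stratification factor 2 so that it matches exclusion 3, and exclude prior MAGE-A3 immunisation in 4.3. This is probably too late: the protocol is dated October 2015, and Appendix A expected recruitment to finish by February 2013. The wider factor would also pool vaccine with interferon and anti-CTLA-4, so it would not by itself balance MAGE-A3 exposure. The adjustment does most of the work.

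The analysis changes remain feasible, since section 6.4.2 says that work on existing samples continues after collection stops. They cost one degree of freedom and a little more analysis. The added exclusion might cost a few eligible patients. If no enrolled patient had prior MAGE-A3 immunisation, a sentence saying so settles the point.

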1.2.3.4. Summary of the safety data from previous clinical trials with recMAGE-A3 ASCI

The immunotherapy with recMAGE-A3 appears to be well tolerated. As of February 2008, more than 320 patients have received a total of more than 2,600 doses of recMAGE-A3 combined with 3 different Adjuvant Systems or alone; approximately 500 doses of the MAGE-A3 + AS15 ASCI have been administered to some 60 patients. The AS15 Adjuvant System has also been investigated combined with other antigens in the treatment of patients with prostate cancer or breast cancer.

Most of the adverse events observed in all these studies were to be anticipated and consist of local and systemic symptoms, such as injection site reactions, myalgia and fatigue. These adverse events have mainly been of Grade 1 or 2, but systemic Grade 3 events have occasionally been reported. Except for fatigue, these Grade 3 symptoms have rarely been assessed to be possibly related to the ASCI treatment. Almost all serious adverse events observed in the studies were assessed by the investigators as being unrelated to the study treatment.

Please refer to the Investigator's Brochure for a detailed description of all the clinical studies of the recMAGE-A3 protein and the results in terms of safety, clinical activity and immunological response.

1.2.3.5. Identification of a gene signature being associated with clinical benefit in response to MAGE-A3 ASCI treatment

Microarray gene profiling has been shown to be a powerful technique predicting treatment response or disease relapse in cancer patients, and a number of large scale clinical trials are currently in progress to validate the gene profiles potentially associated with different prognoses [Vantomme, 2004; Weigelt, 2005]. Also in the Phase II melanoma trial (GSK 249553/008), an attempt was made to identify from a tumor biopsy a gene signature that may predict a favorable clinical outcome for patients treated with the recMAGE-A3 + AS15 ASCI [GSK, unpublished].

In this study, tumor samples were tested for gene expression using Affymetrix HU-U133.Plus 2.0 gene chips covering about 47,000 transcripts. Biopsies from 69 patients were tested. In a first step, a supervised comparison was performed in order to find a group of genes able to cluster 11 patients considered as presenting clinical benefit (complete response, partial response, mixed response or stable disease) in one group, and 11 patients with progressive disease in the other group. From this analysis, 41 differentially expressed probe sets (34 genes) that could segregate the patients with progressive disease and the patients with clinical activity were selected. In a second step, these 41 probe sets were used with the gene expression data from 69 patients to predict their clinical status in a hierarchical clustering approach. As a result, 2 clusters were clearly identified: one associated with patients who have progressive disease, and another one associated with clinical benefit. Interestingly, mixed-responders and patients with stable disease clustered with the group of objective responses, suggesting an association between the gene signature and a favorable clinical outcome following the MAGE-A3 ASCI treatment.

Estimated Kaplan-Meier (KM) curves of the Time to Treatment Failure for the recMAGE-A3 + AS15 group of patients from the GSK 249553/008 melanoma trial also suggest that the presence of the gene signature correlates with a favorable clinical benefit in response to the recMAGE-A3 + AS15 therapy. In the GSK 249553/004 Phase II study of stage IB/II MAGE-A3 positive NSCLC patients, the same gene signature was found to be predictive of clinical activity. In both settings (metastatic melanoma and primary NSCLC tumor), approximately 50% of patients present with this predictive gene signature.

This set of genes differentially expressed in patients with clinical benefit in response to the MAGE-A3 ASCI treatment will in this protocol be referred to as the predictive gene signature. Overall, it is considered that selection of NSCLC or melanoma patients with MAGE-A3 positive tumors presenting with the predictive gene signature may increase the efficacy of treatment with recMAGE-A3 ASCIs by a factor of 2. Based on the gene profile data, GSK Biologicals has initiated a Phase II trial to prospectively validate the identified gene signature as a predictive marker of the clinical outcome for patients with unresectable stage III or stage IV M1a disease treated with the recMAGE-A3 + AS15 ASCI.

1.2.4 Rationale for the use of Poly IC:LC in combination with recMAGE-A3 + AS15 ASCI

Polyinosinic-Polycytidylic acid stabilized with poly-L-lysine and carboxymethylcellulose (Poly-ICLC) is a synthetic double-stranded ribonucleic acid (dsRNA) with broad immune-enhancing effects. These effects include induction of interferons (IFNs) and other cytokines, activation of cellular immunity (T4 cells, natural killer [NK] cells, and macrophages), an immune adjuvant effect, and activation of several nuclear enzyme systems (oligoadenylate synthetase [OAS] and the dsRNA dependent p68 protein kinase [PKR]) involved in antiviral and antitumor host defenses. More recently it has been shown to have broad gene regulatory actions as well.

Poly-IC:LC is a Toll-like receptor 3 agonist (TLT3) has been under clinical investigation since the 1970s, including human trials for a wide variety of neoplastic, viral, and neurologic conditions [Levy 1975, Levy 1984, Levy 1992; Houston 1976, Carter 1987]. The original US IND, held by [name], investigated dose levels of greater than 100 µg/kg of Poly-ICLC.

CONFIDENTIAL

A separate IND, No. 43,984, was opened in 1995 under which 6 clinical studies have thus far been conducted in approximately 350 glioma or glioblastoma patients. Dose regimens used in these trials generally consisted of 20- $\mu\text{g}/\text{kg}$ Poly-ICLC 3 times each week. The degree of adverse effects seen with of Poly-ICLC depends on 3 factors: (1) dose, (2) route of injection, and (3) health status of the patient. Early phase 1 studies were done to determine the maximum tolerated dose, under the assumption that this was also the most effective dose. In these studies of cancer patients, it was found that the maximum tolerated dose was about 12 mg/m^2 when given intravenously in patients who were not terminally ill. Patients typically developed fevers of 40°C, myalgias, arthralgias, malaise, and some nausea and vomiting. Fever was the primary dose-limiting factor. At this dose, the mean serum interferon level was 2000 IU/mL. While the dose of exogenous interferon rarely attains this level, levels of 100 IU/mL after exogenous interferon are associated with the same adverse effects as those in high-dose Poly-ICLC. In most of the early cancer trials, doses around 6 mg/m^2 of Poly-ICLC IV were generally used. Mild (grade 1), transient (less than 7 days) hepatic enzyme elevations were described in a trial of 100 $\mu\text{g}/\text{kg}$ Poly-ICLC given intravenously in multiple sclerosis patients. In 3 patients, the elevated enzyme levels were prolonged for greater than 7 days, but in all patients, the enzyme levels returned to normal after temporary discontinuation of the Poly-ICLC. One paralyzed multiple sclerosis patient in this group suffered a fatal pulmonary embolus that was not judged to be due to the drug. Poly-ICLC has been associated with a coagulopathy in dogs, but not in other species (including primates); and there has been no change in the expected incidence of deep venous thrombosis, pulmonary embolus, or coagulopathy in multiple sclerosis, AIDS, or malignant glioma patients on low-dose intramuscular Poly-ICLC. It was subsequently shown that a low dose of Poly-ICLC was better than a high dose for enhancing immune effects, and that the higher dose actually inhibited a number of cell-associated immune functions. It was also found that intramuscular injection brought about much milder side effects. Representative safety data in humans at a dose of 20- $\mu\text{g}/\text{kg}$ Poly-ICLC 3 times each week have been reported in 2 clinical trials: Protocol NABTC 01-05 entitled: "An open multicenter trial of Poly-ICLC treatment of newly diagnosed glioblastoma with Poly-ICLC as an adjuvant to external beam radiation" and Protocol NABTC 01-06 entitled: "An open multicenter trial of Poly-ICLC in subjects with recurrent anaplastic glioma." Treatment with Poly-ICLC in these 2 clinical trials appeared to be well tolerated; adverse reactions were usually mild or moderate in nature (grade 1 or 2 by the National Cancer Institute Common Terminology Criteria for Adverse Events scale).

Toll like receptor agonists have been shown to be effective adjuvants and in pre-clinical models poly IC:LC has been shown to be an effective booster of immunity when added to a peptide vaccine. Celis and colleagues have shown that in melanoma mouse models that polyIC:LC is a potent adjuvant for a peptide vaccine with the addition of an anti-CD40 antibody, or with the addition of other type TLR agonists (Cho and Celis, 2009, Wells et al, 2008)). Studies in infectious disease vaccine models have confirmed the synergy of multiple TLR agonists within a vaccine strategy (Raman al 2010), Different TLR agonists signal via different pathways, again suggesting that combinations of TLR agonists may induce optimal immune responses (Agrawal et al, 2003). Based on the compiled data in which different TLR agonists have been shown to have immunostimulatory activity, it was felt that the combination of the TLR 3 agonist poly IC:LC with ASCI, which contains a CpG ODN TLR9 agonist, was rational.

Based on the doses used in the above trials, and the side effect profile of the drug, a single 1000 μg dose of Hiltonol will be used subcutaneously in the same limb as the recMAGE-3 + AS15 ASCI injections are given. As a function of surface area, the Human Equivalent Dose of 1000 μg

of Poly-ICLC corresponds to 5-10µg in the mouse, which is a dose that has marked immunomodulatory effects in multiple animal models. For further details of preclinical safety and toxicology tests of Poly IC:LC, see the Investigator's Brochures.

1.3. Rationale for the study: relapse of patients with resectable stage IV melanoma after surgery

Surgery of stage IV melanoma is not generally curative and approximately 90% of the patients will ultimately die of metastatic disease [Markovic, 2007]. There is thus a need for adjuvant therapy to prevent disease relapse after surgical resection of the primary tumor. The role of chemotherapy as adjuvant treatment remains unclear with no tangible benefit in terms of prolonged overall survival [Nathan, 1995]. Non-specific immunotherapy with high-dose interferon has shown activity on disease-free survival, but its impact on overall survival in stage III resected melanoma is less clear, and there is simply no track record for interferon in resected stage IV melanoma [Garbe, 2001]. Low dose Interferon has been investigated in several studies with patients with stage III disease and did not show any significant improvement in Relapse-Free Survival or Overall Survival. The recent Phase III trial with pegylated interferon showed a significant long-term impact of this treatment on relapse-free survival, but not on overall survival in resected stage III disease [Eggermont, 2007]. Subgroup analyses in this study further showed that patients with macroscopic lymph node involvement did not derive a significant clinical benefit from this treatment, warranting the development of new treatment options for these patients. Active immunization against tumor antigens is certainly one such possible approach.

The recMAGE-A3 ASCI has shown promising results in Phase II studies: In the recent Phase II proof-of-concept trial of two different formulations of the recMAGEA3 ASCI in melanoma patients with early metastatic disease (GSK study 249553/008), a strong and robust immunological response was seen, and the safety of the treatments was considered acceptable, raising no specific safety concerns. Objective clinical response was observed for 5 of the 75 patients treated and another 7 patients showed disease stabilization (over periods varying between 5 and 12 months, some still ongoing). These preliminary findings support the development of the recMAGE-A3 ASCI in the adjuvant melanoma setting, particularly in the stage IV NED setting in which microscopic residual disease makes relapse of disease likely within a year of surgical resection.

Additional support for developing the recMAGE-A3 ASCI in the adjuvant melanoma setting may be found in the Phase II proof-of-concept trial of the recMAGE-A3 ASCI as adjuvant therapy for patients with resectable stage IB and II NSCLC. This study (GSK 249553/004, see Section 1.2.3.2) showed a relative reduction of the risk of disease recurrence of 27% in the group receiving the ASCI compared to the placebo group. The immunological responses observed in melanoma patients and NSCLC patients in the adjuvant and metastatic settings, respectively, are very similar, so it is reasonable to expect that an equivalent tumor response will be seen in the adjuvant resected stage IV melanoma setting.

The justification for adding Poly IC:LC as an adjuvant to recMAGE-A3 + AS15 ASCI are data suggesting in pre-clinical murine models that the use of two different TLR Agonists added to a

vaccine or other immunotherapy approach can augment its anti-tumor activity and immunogenicity, as cited in section 1.2 above. Since the AS15, containing CpG709 and MPL that are a TLR 9 and TLR3 agonists respectively, is well tolerated when added to a recMAGE-3 ASCI, and the Poly IC:LC is a TLR3 agonist that is quite well tolerated as well, the addition of the different agonists seems sensible and is likely to be safe and well tolerated.

Taking into account the tumor-specificity of MAGE-A3, the MAGE-A3 expression levels in stage IV melanomas, the acceptable tolerability of the recMAGE-A3 + AS15 ASCI and promising results from Phase II proof-of-concept trials (GSK 249553/008 and 249553/004), it is proposed to initiate a randomized Phase II trial to evaluate the immunogenicity, safety and tolerability of the recMAGE-A3 + AS15 ASCI with or without TLR 3 agonist Poly IC:LC in patients with stage IV resected melanoma at very high risk of relapse.

